## 1. Background Information

### 1.1 Name, Description and Intended Use of the Test and Control Articles (Treatments)

The single investigational test article, ZuraPrep™ solution [REDACTED] [REDACTED] is being evaluated for efficacy as a preoperative skin preparation solution by demonstrating its immediate and persistent antimicrobial properties. Testing will be performed based upon procedures outlined in the FDA Tentative Final Monograph (TFM) for Health-Care Antiseptic Drug Products (vol. 59, No. 116, June 17, 1994, pp. 31450-31452) and ASTM E1173 – 15 Evaluation of Preoperative, Precatheterization, or Preinjection Skin Preparations.

ZuraPrep™ Vehicle [REDACTED] [REDACTED] will be evaluated as a negative control.

ChloraPrep® [REDACTED] (Scrub Teal® Tint) will be evaluated as a reference control.

### 1.2 Risk/Benefit Summary

There are minimal anticipated adverse health risks for the participants of this study. Considerable safety and efficacy data are available for the active ingredient in the test and reference formulations.

### 1.3 Treatment Application Configurations

The treatments will be applied topically to intact skin of the abdomen and groin regions of each subject. The treatments will be applied per the Treatment Application Instructions (Appendix 14.7).

### 1.4 Good Clinical Practice and Regulatory Requirements

This study will be conducted in compliance with this protocol, Good Clinical Practice (GCP) including 45 CFR 160 and 164 (Authorization for Use/Disclosure of Protected Health Information (PHI), 21 CFR 50 (Protection of Human Subjects), 56 (Institutional Review Boards), 330 (Over-The-Counter Human Drugs which are generally recognized as safe and effective and not misbranded) and Tentative Final Monograph for Health Care Antiseptic Drug Products (TFM), the Standard Operating Procedures of MicroBioTest, the study protocol and any protocol amendments.

### 1.5 Study Population

Healthy male and female volunteers, 18 years of age or older, with no dermatological conditions or known history of sensitivity to natural rubber latex, adhesive skin products (e.g., Band-Aids, medical tapes), isopropyl alcohol or chlorhexidine gluconate will be enrolled into this study. For this trial, a sufficient number of volunteers will be recruited in the screening phase such that a total of at least 320 abdominal (sebaceous poor) regions and 320 groin (sebaceous rich) regions are evaluable at the completion of the study for the test article and reference article, and a total of at least 64 abdominal regions and 64 groin regions are evaluable at the completion of the study for the negative control. Subjects must satisfy all Screening Day and Treatment Day Inclusion/Exclusion Criteria prior to screening sample collection and Treatment Day procedures.

The right and left sides of both the abdomen and the groin must meet the minimum Screening Day baseline values stated in the Inclusion Criteria to qualify for the study.

At least 352 human subjects will be employed utilizing bilateral applications assuring that the treatments will be evaluated on the sites as described in the following table:

Table 1.5: Minimum number of readings per anatomical site (abdomen and groin), per treatment, per sampling interval (30 seconds, 10-minutes, and 6 hours post-application)		
Treatment	Number of Abdomen Evaluations	Number of Groin Evaluations
ZuraPrep™ [REDACTED]	320	320
ChloraPrep® [REDACTED], Scrub Teal® Tint (positive/active control)	320	320
ZuraPrep™ Vehicle, [REDACTED] (negative/inactive control)	64	64

### 2. Study Objectives and Purpose

The primary objective of this study is to measure the antimicrobial effectiveness of a single investigational test article, ZuraPrep™ [REDACTED] as specified by the TFM, updated by recent procedures specified by the Food and Drug Administration Center for Drug Evaluation and Research. At 10 minutes post-prep the test article should achieve a 70% responder rate, as defined below, to be considered a therapeutically effective antimicrobial agent. Additionally, subjects will be evaluated at 30 seconds and 6 hours post-prep as a secondary endpoint. A positive and negative control will be evaluated using the same methodology.

### 3. Study Design

#### 3.1 Study Type

This is a randomized, paired-comparisons design where each subject receives two of the planned treatments.

**Table 3.1:** Treatments, Anatomical Sites of Evaluation, Application and Dry Times and Coverage Areas (See Appendix 14.7 for detailed application instructions)

Treatment (Quantity/Volume)	Body Site	Application Time	Dry Time	Area of Coverage
ZuraPrep™ [REDACTED]	Abdomen (sebaceous poor)	30 seconds	3 minutes	5" x 5"
	Groin (sebaceous rich)	2 minutes	3 minutes	1.5" x 5"
ChloraPrep® [REDACTED] Scrub Teal® Tint, (positive control)	Abdomen (sebaceous poor)	30 seconds	3 minutes	5" x 5"
	Groin (sebaceous rich)	2 minutes	3 minutes	1.5" x 5"
ZuraPrep™ Vehicle, [REDACTED] (negative control)	Abdomen (sebaceous poor)	30seconds	3 minutes	5" x 5"
	Groin (sebaceous rich)	2 minutes	3 minutes	1.5" x 5"

#### 3.2 Primary Endpoint/Analysis

The study will be analyzed per the standards of the 1994 Tentative Final Monograph (TFM) for Effectiveness Testing of a Patient Preoperative Skin Preparation (FR 59:116, 17 June 94, pp. 31450-31452), as updated by recent recommendations by the FDA on responder rates. The primary efficacy criteria will be assessed based on  $\log_{10}$  CFU/cm^2 reductions at the 10-minute sampling time. The TFM indicates  $\log_{10}$  CFU/cm^2 reductions as the primary efficacy measure while the Proposed Amendment of the Tentative Final Monograph (FR 80:84, 01 May 2015) indicates responder rates as the primary efficacy requirement. This study will use responder rate at 10 minutes post-prep as the primary measure of efficacy but will also calculate and show  $\log_{10}$  CFU/cm^2 reductions from baseline.

The primary measure of antimicrobial efficacy is the reduction of skin flora on the abdominal and groin sites at 10 minutes following application of the study treatments relative to the Treatment Day baseline counts.

The reduction will be calculated by a percent successes approach (i.e. percent of subjects meeting required reductions = responder rate). A site is considered a responder for the treatment at the indicated time point if the criteria in the following table are met:

Table 3.2: Minimum and Maximum Treatment Day Baseline and Expected Mean Log10 Reduction per Anatomical Site		
Anatomical Site	Minimum and Maximum Treatment Day Baseline*	Expected Mean Log10 Reduction
Abdomen	$1.0 \times 10^3 - 3.2 \times 10^5 \text{ CFU/cm}^2$ (3.0 Log 10 – 5.5 Log 10 )	2.0 log 10 @ 10-minutes
Groin	$1.0 \times 10^5 - 3.2 \times 10^7 \text{ CFU/cm}^2$ (5.0 Log 10 – 7.5 Log 10 )	3.0 log 10 @ 10 minutes

\*Note: For the Screening Day baseline, the maximum upper limit does not apply. Only the minimum criteria must be met.

Responder status will be calculated separately for the abdomen and groin, for each test substance, for each post-treatment sample time, and for each subject. The individual responses will then be grouped to generate an overall responder rate for each anatomical area, for each test substance, and for each post-treatment time. The primary efficacy goal for active products is to have the lower bound of the 95% confidence interval for the responder rates at 10 minutes to be greater than or equal to 70%.

### **Secondary Endpoints/Analysis**

Responder rates at 30 seconds will be calculated identically to the 10 minute rates. At 6 hours a site is considered a responder if it is below baseline; otherwise, 6-hour responder rates will be calculated identically to the 10-minute responder rates. The secondary efficacy goals are to have the 95% confidence intervals for the responder rates to be greater than or equal to 70%. Log10 CFU reductions from baseline will also be calculated for all post-prep samples.

### **Study Validity**

For a valid study, the active control must make the same objectives that the test article does and both the test article and the active control should be superior to the inactive control for the primary endpoint. The responder rates for both active and inactive treatments at 6 hours are near 100%. Therefore, comparison of responder rates at 6 hours is unlikely to show any difference. Differences in log10 CFU/cm^2 reductions from baseline will be used at 6 hours in order to show that the active treatments are more effective than the inactive control.

### 3.3 Randomization and Blinding

Subjects will be randomized before treatment, after screening eligibility is determined. Subjects will be randomized to treatment using the following block design:

#### Treatment Balance

Each subject will receive two different treatments, one on the right side of the body and one on the left.

The treatment assignments will be balanced such that the number of readings per anatomical site matches the calculated requirements.

#### Left/Right Balance

The application will be randomized so that each treatment is used on an equal number of left and right sides of the body.

#### Site and Sample Time Balance

Within each anatomical site, sampling order will be randomized for baseline, 30 second, 10 minute, and 6 hour samples based on the statistical consultant's randomization plan.

The randomization plan has been updated [REDACTED]

The Investigator is responsible for ensuring that the randomization is followed. A basic outline of a randomization schedule for the abdominal and groin sites is provided in Appendix 14.4. The final randomization schedule will be prepared before the initial treatment. The test and control articles will be labeled with the appropriate codes as designated by the study randomization.

Subjects will be identified by their initials, a screening ID number, and a subject number corresponding to each body region in the study for which they qualify. Subject numbers will not be assigned until a subject has passed the screening criteria, including baseline bacterial counts (at least  $1.0 \times 10^5$  CFU/cm^2 in the groin and at least  $1.0 \times 10^3$  CFU/cm^2 on the abdomen). Subjects whose abdominal and groin regions qualify will be assigned the subject number. Therefore, for each of the participating subject will be assigned two identification numbers.

- Screening subjects will be assigned numbers ranging from 9001 to 9999.
- Subjects to be treated (including treatment day baseline collection) will be assigned sequential numbers ranging from 0001 up to the total number of test subjects treated.

The study materials will not be blinded from the Investigator or other study staff performing the study material application or bacterial sample collections. The staff member(s) performing bacterial enumeration will be blinded from the identification of treatment assignment. The study staff performing the bacterial enumeration will not be involved in the study material application or the collection of samples. The Raw Data Sheet sections of the case report form will be maintained separately (from the pages within the case report form which include study treatment identifications) during the conduct phase of the study. The study staff performing the bacterial enumeration will record counts directly onto the Raw Data Sheet pages of the case report form without accessing the subject study documentation folder containing the other case report form pages. The Raw Data Sheets will be compiled with the entire case report form after all data recording has been completed. The CRF will serve as the source document.

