### **5.1.2 Treatment Phase Study Procedures**

A sufficient number of subjects who meet the entrance criteria will be enrolled into the treatment phase of the study for each region, such that the total number of abdominal regions and the total number of groin regions meets or exceeds the number required (320 abdominal regions and 320 groin regions for the test article and reference article; and 64 abdominal regions and 64 groin regions for the negative control). The randomization schedule will designate the treatment to each side of the abdomen and groin.

The Treatment Day Inclusion/Exclusion Criteria CRF will be completed. If these criteria are satisfied, a visual skin assessment will be performed to evaluate the condition of each test area.

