##### **5.1.2.1.1 Preparation of Abdominal Test Area**

The test site within the abdominal region (abdominal test area) is defined as the area below the umbilicus and above the groin. Using a 5" x 5" sterile template, the corners of each abdominal test area will be marked directly on the skin using a non-toxic skin marker. Four sampling sites will be numbered within each abdominal test area, on each side of the abdominal region. The positioning and numbering of the abdominal sampling sites are standard for all subjects. Sampling sites on the contra-lateral side of the abdomen will be numbered in a mirror-image orientation. The four

sampling sites within each abdominal test area represent one baseline (pre-prep) site, and one post-prep sampling site for each of three sampling times (30 seconds, 10 minutes, and 6 hours).

Prior to performing the Treatment Day baseline sample collection, a skin irritation assessment will be performed.

If an irritation score of 1 for any individual skin condition at the Treatment Day baseline is assigned, the subject will be excluded from the treatment phase of the study. After abdominal test areas are marked and sample sites numbered, baseline samples will be collected from the appropriate site per the randomization schedule (Appendix 14.4) in each test area using the scrub cup technique.

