#### **5.1.2.2 Treatment Materials Application**

Following baseline sample collection, randomly assigned contralateral test areas will be treated with the applicable treatment materials. The post-application sampling times will be randomized among the sampling sites within a test area.

The treatment materials will be applied and the sampling configurations will be performed per the Randomization Schedule (Appendix 14.4) and the Study Material Treatment Application Instructions (Appendix 14.7). The duration of each application procedure will be recorded on the appropriate CRF.

The applicator weight [REDACTED]

[REDACTED] will be measured and documented before and after application to the treatment site. See Appendix 14.7 for details.

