#### 14.4 Randomization Scheme

##### Abdominal and Groin Sites Bilateral Sampling Procedure Configurations

###### GROUP 1

Key: A = ZuraPrep™ [REDACTED]  
B = ChloraPrep® [REDACTED]ator (Scrub Teal® Tint)  
C = ZuraPrep Vehicle (negative control)

Subject	Treatment	Site 1	Site 2	Site 3	Site 4
0001					
0002					
0003					
0004					
0005					
0006					
0007					
0008					
0009					
0010					
0011					
0012					
0013					
0014					
0015					
0016					
0017					
0018					
0019					
0020					
0021					
0022					
0023					
0024					
...					

Subjects will be numbered sequentially from 0001 to the number of subjects treated during the study.

Randomization will be performed by group issued prior to study initiation.

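### The product/side assignment is not concealed from the unblinded sample collectors until the Treatment Day baseline samples have been taken

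*Combined protocol and SAP*

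**What the plan says.** **Who is blinded (section 3.3).** "The study materials will not be blinded from the Investigator or other study staff performing the study material application or bacterial sample collections". The protection is at the plate-reading stage: "The staff member(s) performing bacterial enumeration will be blinded from the identification of treatment assignment".

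**When assignment is made.** Section 3.3 says: "Subjects will be randomized before treatment, after screening eligibility is determined". Numbering covers the baseline step: "Subjects to be treated (including treatment day baseline collection) will be assigned sequential numbers ranging from 0001" upward. Appendix 14.4 says: "Randomization will be performed by group issued prior to study initiation".

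**What the schedule holds.** Section 5.1.2 says: "The randomization schedule will designate the treatment to each side of the abdomen and groin". The outline grid in Appendix 14.4 has a treatment column and four site columns in the same row for each subject, under a key that decodes A, B and C.

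**How baseline is taken.** Section 5.1.2.1.1 says that, once areas are marked, "baseline samples will be collected from the appropriate site per the randomization schedule (Appendix 14.4) in each test area using the scrub cup technique". Section 5.1.2.1.2 does the same for the groin. Section 5.2.1 describes the sample as two one-minute hand scrubs, pooled, with pressure described only as moderate.

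**When product is needed.** Section 5.1.2.2 says: "Following baseline sample collection, randomly assigned contralateral test areas will be treated with the applicable treatment materials".

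**What baseline does.** In section 8.2.1 every change is baseline minus a later value, and responder status follows from that change. In section 8.1 a body site enters the mITT set only if its Treatment Day baseline qualifies.

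**The concern.** Visible differences between products may make blinding after application hard. Before application nothing stands in the way: position, not product, is all that the collector needs. Yet the plan points an unblinded collector to a document that carries both.

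Each subject receives two different products on opposite sides, so the same operator may scrub both sides while able to know which is which. Left/right balancing (section 3.3) cancels a handedness effect. It does not cancel an effect that follows the product. Blinded plate counters cannot correct a difference made at collection.

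A slightly higher baseline recovery on one product's side adds the same amount to that product's log10 reduction at 30 seconds, 10 minutes and 6 hours. It can also carry a site over the mITT minimum, or past the maximum and out of the set.

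**Working it through.** **1. Is the assignment concealed before baseline?** The sections quoted above fit together as follows.
- The collector is unblinded (3.3).
- The collector must consult the schedule for the baseline position (5.1.2.1.1, 5.1.2.1.2).
- The schedule designates the product by side (5.1.2, Appendix 14.4).
- Product is applied afterwards (5.1.2.2).
- No readable section provides sealed assignments, a split schedule or delayed release.

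So concealment up to baseline is not provided for. When staff actually see the assignment is not stated.

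**2. The plan's own sample size (section 8.3).** Inputs: p0 = 0.70, p1 = 0.778, power 80%; two-sided 5% assumed. The method is redacted.
- Score formula: n0 = [(1.96·√(0.70·0.30) + 0.842·√(0.778·0.222)) / 0.078]², which gives 256.
- With continuity correction: n = (n0/4)·[1 + √(1 + 2/(n0·0.078))]², which gives 269.
- The stated 267 is close to this. An exact rule at 267 needs 202 responders and has power 82.1%.

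**3. Pass rule at n = 320.** Section 8.2.1 specifies exact intervals, and section 3.2 requires a lower bound of at least 70%.
- 241/320 (75.3%) has lower bound 70.2%, which passes. 240/320 has lower bound 69.9%, which fails.
- P(X ≥ 241 | 320, 0.70) = 2.1%. P(X ≥ 241 | 320, 0.778) = 87.2%.

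**4. Sensitivity to a product-linked baseline shift.** The documents give no SD, so assume normal log10 reductions with SD 0.8, 1.0 or 1.3 and a uniform shift d on one product's sides. The apparent rate is Φ(z + d/SD), where z = 0.524 for a true rate of 70%. The chance of passing is P(X ≥ 241 | 320, apparent rate).

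| d (log10) | SD | Apparent rate, truth 70% | Chance of passing |
|---|---|---|---|
| 0 | any | 70.0% | 2.1% |
| 0.1 | 0.8 | 74.2% | 35% |
| 0.1 | 1.0 | 73.4% | 24% |
| 0.1 | 1.3 | 72.6% | 15% |
| 0.2 | 0.8 | 78.1% | 89% |
| 0.2 | 1.0 | 76.6% | 73% |
| 0.2 | 1.3 | 75.1% | 50% |

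For a product truly at 77.8% (z = 0.765), d = 0.1 gives an apparent 80.0% to 81.3%.

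These figures are for one body area. Abdomen and groin are assessed separately.

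**5. The ATE criteria (Amendment 6).** These regress the post-treatment count on treatment and baseline. If the fitted baseline slope is b, a shift d on one product's side moves the adjusted difference by about b·d. A responder-rate analysis takes the full d.

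**6. Effect of the fix on size.** None: (320 + 320 + 64)/2 = 352 subjects, as planned.

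**The case against.** **The documents do not show that staff know the assignment at baseline.** A reader might infer that they do. Section 3.3 says that the materials are unblinded, not when the side assignment is seen. Appendix 14.4 is described as a basic outline, the final schedule is prepared later, and a note on an updated plan is redacted. The working layout cannot be seen. This stands: early sight is permitted by the text, and made likely by it, but not documented.

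**Eligibility is a weak route.** A reader might also infer that unblinded staff control Treatment Day eligibility with the assignment in hand. The text does not support that. Irritation is scored before the schedule is needed (5.1.2, 5.1.2.1.1, 5.1.2.1.2). An irritation exclusion removes the whole subject, both sides (7.2). Readings of 320/320/64 over 352 subjects imply 288 test-reference pairs and 32 of each vehicle pair, so 288/352 = 82% of subjects would lose one test and one reference side. The baseline-count criterion is read after treatment by blinded counters (3.3, section 4), although the collector can influence the count.

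**The size is hypothetical.** The calculation needs a same-direction shift across a product's sites, while the scrub is timed, repeated and done by trained staff. A firmer scrub can also push a site above the baseline maximum. These points stand, and the figures show sensitivity only.

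**The fix closes part of the channel.** The same unblinded staff take the post-application samples, and a lighter scrub there shifts the reduction equally. This is true, but it is no reason to leave open the part that can be closed.

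**Conclusion.** The point holds as a gap in concealment. The protocol sends unblinded collectors to a schedule carrying the product for each side before they take an operator-dependent sample that underlies every responder result and mITT entry, and no readable text withholds the product until afterwards.

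Under the stated assumptions (normal reductions, SD 0.8 to 1.3, n = 320, one body area), a 0.1 log10 product-linked shift raises the chance of a false pass at a true 70% from 2.1% to 15-35%. This is neither evidence that a shift occurred nor the amount that the fix is shown to save. The ATE criteria are exposed only through the baseline slope. The documents do not support a claim that staff demonstrably knew the assignment, that they could steer eligibility by side, or that the remedy is free. The change is worth making because it acts directly on the primary endpoint at small cost.

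**What to change.** - Split the schedule for each subject. Staff use a sampling-position sheet, with no product or side assignment, for irritation scoring, marking and baseline collection.
- Keep the product/side assignment sealed until Treatment Day clinical eligibility is signed and all four baseline samples are collected. Record the opening time on the CRF.
- Amend section 3.3 so that the open-label statement applies only after baseline collection.

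**Cost.** Reformatting and sealing the schedule, one CRF entry, and a short delay before application while applicators are identified and weighed (section 5.1.2.2 already requires weighing). Post-application sampling windows are unaffected, because their clock starts after application and drying (5.1.2.3). Sample size and power do not change. Possible bias in post-application sampling remains and needs separate consideration.

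Amendment 6 was issued after testing was complete. For data already collected, the final report should therefore state when collectors had access to the assignment.
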